#### B. Feasibility:

The following feasibility data will be collected and assessed :

- 1) Recruitment:
  - a. Recruitment sites (number, location, and method of their selection)
  - b. Factors influencing recruitment rate
  - c. Methods used for subject recruitment
  - d. Number of subjects:
    - i. Initially contacted
    - ii. Initial interviewed

- iii. Consented
- iv. Baseline data collected
- e. Reasons for non-participation:
  - i. After initial contact and/or initial interview
  - ii. After consent process
  - iii. After initial data collection or throughout the study
  - iv. Until end of study
- f. Reasons for participating in and completing study

2) Randomization:

- a. Testing effect of randomization process on distribution of demographic, co-morbidity, and other background characteristics
- c. Testing randomization process on their baseline main outcomes
- d. Examining acceptability of the randomization process and its effect

3) Missing data:

- a. Differences in rates of missing data between medication and placebo groups and per time point
- b. Pattern of missing data

4) Retention rate:

- a. Differences in retention between medication and placebo groups
- b. Factors influencing these differences

5) Subjects' satisfaction with:

- a. Study procedures
- b. Study implementation and staffing
- c. Medication delivery methods
- d. Data collection timepoints and outcomes

6) Medication fidelity with:

- a. Delivery methods
- b. Number of successful and failed deliveries
- c. Assessment methods
- d. Timing and method of feedback

7) Study improvement procedures/maintaining documentation of:

- a. Study/protocol development, revision, and modification
- b. Issues and concerns with implementing recruitment strategies
- c. Issues and concerns with accessing, distributing, and tracking of medication and placebo
- d. Issues and concerns with measurements:
  - i. Number of measurements
  - ii. Time requirements of measurements
  - iii. Redundancy among measurements
  - iv. Positive or negative carryover

Sub-study 1b: mQFPD vs. placebo in acute COVID-19 patients.

The primary objectives of this study are:

- Ascertainment of safety of FoTv and
- Assessment of feasibility of the intervention (with the primary outcomes focusing on determination of the rates of recruitment and completion)

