### **Sub-studies 1a and 1b**

Once enrolled, all study participants will receive a package containing the following:

- 14 day supply of study medication (capsules containing either FoTv or mQFPD or placebo)
- Digital thermometer
- Urine pregnancy test (for women of child bearing potential)
- Written instructions on proper usage of study medication
- Paper study daily diary, to include daily medication diary, symptom scores, and temperature/BP measurement data
- A blood pressure cuff or glucometer will be provided to study subjects who require but do not possess one. The study participants are not responsible for lost, stolen, or damaged devices

The study package will be sent via local courier or phlebotomist who will coordinate directly with the study participant to complete delivery. Missed doses will be logged in the provided medication diary, remain unused, and be accounted for at the end of the study. Participants will continue to make every effort to maintain quarantine through vigorous hand washing and appropriate self-isolation measures. All study participants will also receive instruction to strictly avoid alcohol, cannabis, and dairy products during the study period.

During the trial period, participants will be verbally instructed on proper usage of study product, asked to take their temperature twice daily until they reach two consecutive afebrile readings. Participants with prior hypertension will also be required to take daily home measurements of their blood pressure and report any measurements of SBP <90 or >150, or DBP >90 directly to the study team. Any measurements of SBP below 80 or above 180 will be advised to seek immediate medical attention (as specified in Section 15). Participants with prior diabetes will take daily morning glucose measurements and report any blood glucose measurement >200 directly to the study team. Any measurements of blood glucose below 70 will be advised to eat a carbohydrate rich food and report to the study team, and measurements persistently below 70 will be advised to seek immediate medical attention as an immediate priority prior to reporting to the study team. Participants with congestive heart failure or using diuretics will take daily morning weight measurements using a home scale and report to the study team any weight change greater than 3 lbs (1.5 kg) during the study period.

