##### **Baseline:**

The following laboratory assays will be conducted to establish baseline values for safety measures:

- Complete Blood Count with Differential
- Ferritin
- D-Dimer
- Lactate Dehydrogenase
- C-Reactive Protein
- Troponin
- T-cell differentiation panel
- Additionally, plasma, serum, and whole blood will be collected and banked for cytokine, immunological, and metabolomic assays.

Please note that nasal swab or salivary samples will be collected at day 0 (baseline) as well as at days 7 and 14 for all subjects.

A urine home pregnancy test will be delivered to women of childbearing potential and the results will be self-reported to the study team prior to starting study medication.

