required methodological modifications. The safety data will be summarized by treatment group and site. Adverse events will be tabulated. These will include the number of participants for whom the event occurred, the rate of occurrence, and the severity and relationship of adverse events to study treatment. Safety data will be analyzed using ANOVAs for continuous variables and Chi-square analyses for dichotomous variables at each time point. Wilcoxon-Mann-Whitney rank-sum test will be used to analyze treatment arm versus control arm across study visits and sites. We anticipate using non-parametric tests because the majority of the outcome measures used in our research may not be normally distributed. The Kruskal-Wallis test will be used to determine whether samples from each of the two arms originated from the same distribution. Since nonparametric tests are based on complete data and ignore missing follow-up data, general linear mixed regression modeling (Gibbons et al, 1988; Hedeker et al, 199; Laird et al, 1982) will be used to confirm the results of the nonparametric tests. The two arms will be compared over time with a focus on the treatment by Time interaction effect. Mixed regression modeling offers robust handling of missing data (Little, 1996) with an assumption that the data is missing at random. This method allows the inclusion of subjects with missing data or those who were terminated early in the study, without relying on data imputation procedures. This method provides an estimate of the individual variability around the population trend, the variability of the individual intercepts (baseline values) and slopes (changes across time), and the correlation between them. Co-variance structure will be chosen based on Akaike's Information Criterion (AIC). Random group level treatment effects will also be evaluated for importance based on the model AIC. Denominator degrees of freedom will be calculated using the Kenward-Roger small sample correction.

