A detailed list of feasibility outcomes is provided in the previous section. Briefly, feasibility outcomes will be assessed by determining: 1) Numbers of potentially eligible and ineligible patients, number contacted, and consent rates. 2) Feasibility of recruiting sites in which staff are interested in participating in a future main trial. 3) Rate of retention in the trial, including response rates to questionnaires and individual measures. 4) Intervention fidelity and adherence using case report forms and patient-completed personal diaries. 5) Determining the primary outcome measure for the main trial by assessing and comparing sensitivity to change of the measures and other statistical properties, comparing follow-up rates of different methods of data capture and of individual measures, and evaluating which outcome measures best reflect the patients' recovery goals, as identified from the collected data.

As indicated above, the primary aims of our data analytic strategy for sub-studies 1a and 1b will be directed toward examining the safety and feasibility of the treatments. Although it is not our major focus, we also aim to estimate effect sizes to assist in future power calculations. However, recent work by Kraemer (2006) has highlighted important limitations of this aim due to the large standard error surrounding the pilot study effect size. As a result, the primary focus of our analyses will remain on safety and feasibility and we will report our findings with this limitation in mind. Our goal is to collect important data regarding our ability to implement recruitment strategies, and the safety and feasibility of the treatments and measurements. Information derived from this research will lead to better-designed full-scale studies and help inform decisions regarding whether it is worthwhile to commit additional resources to future treatment development. Due to our small sample size, our statistical analytical findings will be interpreted with caution. Sub-study 1c will include sufficient number of subjects to test for treatment efficacy.

Data will be analyzed from all randomized subjects. All statistical tests will be two-tailed. Differences will be considered statistically significant provided a p-value of 0.05 or less is obtained. The significance level for the tests will be adjusted with a Bonferroni correction for multiple comparisons, if needed. Data will be analyzed using SPSS version 27.

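### No safety analysis set is defined: with all randomized subjects as the only stated population, participants who never take a capsule would modestly dilute any excess of adverse events in sub-studies 1a and 1b

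*Combined protocol and SAP*

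**What the plan says.** Section 9, Statistical Methods And Considerations, contains one sentence on the analysis population: "Data will be analyzed from all randomized subjects". It stands beside the rules on sidedness, significance level and software and carries no exception. No safety, treated or as-treated set is defined anywhere in the document.

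On adverse events the same section says what will be tabulated: "These will include the number of participants for whom the event occurred, the rate of occurrence", together with severity and relationship to treatment. It names no denominator and no date from which events count. The test is given as: "Safety data will be analyzed using ANOVAs for continuous variables and Chi-square analyses for dichotomous variables at each time point".

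The sequence in sub-studies 1a and 1b is as follows:

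- Section 9 has participants randomized once eligibility is confirmed.
- The package that follows holds the capsules of the assigned arm and, for women of childbearing potential, a urine pregnancy test. On dispatch: "The study package will be sent via local courier or phlebotomist".
- Under Baseline in the laboratory section, the urine test is delivered and "the results will be self-reported to the study team prior to starting study medication".
- Section 6, B. Feasibility, lists "Number of successful and failed deliveries" among the items to be recorded, for both 1a and 1b.

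Section 9 states safety as a primary objective of all three sub-studies.

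**The concern.** Counting everyone randomized protects an efficacy comparison, because non-exposure pulls the estimate towards no effect and so makes a benefit harder to claim. In a safety comparison the same pull makes harm harder to see. A randomized participant who never takes a capsule cannot have a product-related event but still enters the denominator.

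Dosing depends on a delivery that happens after randomization to people who are acutely ill. A delivery may fail. A participant may also deteriorate first, and those hospitalized are told to stop study medication.

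The safety result carries weight here. The synopsis makes the Phase 2 trial conditional on safety and feasibility in 1a and 1b. Section 14 records the regulator's concern that FoTv might accelerate or worsen COVID-19, and the sponsor's reply relies on the Phase 1 safety study to detect such effects.

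**Working it through.** **The plan's own figure.** Sample Size Justification gives 27 per arm plus 6 for 20% dropout. 27 × 1.20 = 32.4, rounded up to 33 per arm and 66 in total, which reproduces. (Dividing instead, 27 / 0.80 = 33.75, gives 34.) No adverse-event rate or power is stated behind the 27, so the base cannot be derived. The allowance is for dropout; the plan gives no figure for participants who are never dosed.

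**Inputs.** From the plan: 33 per arm, equal allocation, "All statistical tests will be two-tailed", and a significance threshold of 0.05. Assumed, because the documents give neither: adverse-event proportions of 10% v 40% and 10% v 30% (placebo v active), and 1 to 6 never dosed of 33 in each arm.

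**Dilution.** Let p_c and p_t be the event proportions on placebo and on product, and f the never-dosed share.

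- If the never-dosed carry the background rate, the active arm shows (1 − f)p_t + f·p_c. Subtracting p_c leaves (1 − f)(p_t − p_c).
- If the never-dosed are recorded as event-free in both arms, the difference is (1 − f)p_t − (1 − f)p_c, again (1 − f)(p_t − p_c).

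The factor does not depend on which case applies. With f = 1/33, (1 − f) = 32/33 = 0.97. With f = 2/33 it is 0.94, with 3/33 it is 0.91, and with 6/33 it is 0.82.

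**Power.** Two-proportion normal approximation with pooled null variance, comparing all randomized (33 per arm, diluted difference) with dosed participants only (33 minus the never-dosed, full difference):

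| Never dosed per arm | Factor | 30-point excess appears as | Power, 10% v 40%: all randomized / dosed only | 20-point excess appears as | Power, 10% v 30%: all randomized / dosed only |
|---|---|---|---|---|---|
| 1 | 0.97 | 29.1 | 0.798 / 0.806 | 19.4 | 0.509 / 0.516 |
| 2 | 0.94 | 28.2 | 0.776 / 0.793 | 18.8 | 0.488 / 0.504 |
| 3 | 0.91 | 27.3 | 0.753 / 0.780 | 18.2 | 0.467 / 0.490 |
| 6 | 0.82 | 24.5 | 0.676 / 0.734 | 16.4 | 0.404 / 0.450 |

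The dosed set restores the full expected difference. It gains about 1 point of power for 1 never dosed, up to 2 for 2, 2 to 3 for 3, and 5 to 6 for 6.

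**Scale against imprecision.** At 10% v 30% with 33 per arm, the 95% half-width of the difference is 1.96 × √(0.10 × 0.90/33 + 0.30 × 0.70/33) = 1.96 × 0.0953 = 18.7 points. Losing 0.6 to 1.8 points to dilution (1 to 3 never dosed) is small beside that.

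**Upper limit with no events.** The one-sided 95% limit is 1 − 0.05^(1/n): 8.7% for n = 33, 9.5% for n = 30. The plan quotes no such limit; this shows only how the denominator changes what could be claimed.

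**Sub-study 1c.** With 133 per arm and 3 never dosed, the factor is 130/133 = 0.977 and power changes by less than 1 point.

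**The case against.** The strongest reply is that the plan never says adverse-event rates use all randomized subjects. The adverse-event text is silent, and the population sentence is a general one. This is fair: the denominator is inferred. But it is the only population offered, and if the text is read as silent, the denominator of a primary outcome is undefined. The same change is needed either way.

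Several stronger readings are tempting, and the documents do not support them.

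- **That some participants will certainly go undosed.** No rate is given. The courier or phlebotomist is to arrange delivery with the participant, failed deliveries are only counted as a feasibility item, and nothing says a failed attempt is final.
- **That post-enrolment pregnancy tests will remove many.** The inclusion criteria for 1a and 1b require a negative serum test at screening, and Reproductive risk in Section 14 places the home urine test at screening too. Such exclusions should be few. These passages disagree on timing with the package list and the Baseline text, and they must be reconciled.
- **That events before the first capsule also bias the comparison materially.** Kits look identical and treatment is blinded, so such events arise alike in both arms. They leave the expected difference in event counts unchanged and mainly add noise, although they can slightly flatten an any-event proportion.
- **That all three sub-studies are equally exposed.** The 1c package contains no pregnancy test, and the feasibility list with failed deliveries belongs to 1a and 1b. A missed vaccination could leave a 1c participant undosed, but the effect there is smaller still.

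It also stands that the plan already promises caution because of the small sample, and that first-dose dates come from participants' own reports.

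**Conclusion.** The point holds in a limited form. Followed as written, the plan applies an all-randomized population to a primary safety question, with no adverse-event denominator or start of counting of its own. In 1a and 1b randomization precedes delivery, so a randomized participant can go undosed, and each one moves the comparison towards no difference. With 1 to 3 never dosed of 33 per arm, 3% to 9% of the true excess is lost, and at most about 3 points of power separate the two analysis sets under the assumed rates. The never-dosed counts and event proportions are assumptions, and the factor presumes a similar never-dosed share in both arms. This is a modest bias in the unfavourable direction. It does not show that the safety comparison is invalid, but a standard remedy is nearly free.

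**What to change.** Add to Statistical Methods And Considerations:

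- Keep all randomized subjects for efficacy and feasibility outcomes.
- Analyse adverse events and safety laboratory tests primarily in randomized participants who took at least one capsule, grouped by product received. State this as the denominator.
- Count adverse events from the first capsule, and list pre-dose events separately by arm.
- Where exposure is unknown because no diary was returned, treat the participant as dosed if delivery was confirmed.
- Report the never-dosed by arm with reasons, and give the all-randomized result as a sensitivity analysis.

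Separately, reconcile the passages on when the pregnancy test is done relative to randomization.

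The cost is a few sentences. The medication diary and the start dates and times on the adverse-event form already supply the data, and the Day 14 bottle photographs in 1a and 1b offer a partial check. The downsides are slightly smaller safety denominators and dependence on self-reported first-dose dates. While the arms stay blinded, leaving out people who were never dosed should add little bias, and the sensitivity analysis will show whether it matters.

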## 10. HUMAN SUBJECTS

Sub-study 1a Fo-Tv vs. placebo:

66 total patients (N=27 in each of two study arms: FoTv and placebo plus an additional 20% per arm to guard against dropout) who have tested positive for COVID-19 and are mildly-to-moderately symptomatic will be included in the study.

### Inclusion Criteria

1. Positive COVID-19 diagnosis within the prior 72 hours or within 9 days of symptom onset
2. Age 18 and older

3. Women of childbearing potential must have a negative urine or serum hCG. Women of childbearing potential must have a negative serum pregnancy test at screening and agree to use contraception throughout the study period.
4. Capable of documenting vitals, symptoms, and study product intake daily and communicating this information to the study team
5. Willing to avoid alcohol, cannabis and dairy products during the study period.

#### **Exclusion Criteria**

1. Any of the following symptoms which, according to the CDC, require hospitalization:
  - a. Trouble breathing
  - b. Persistent pain or pressure in the chest
  - c. New confusion or inability to arouse
  - d. Bluish lips or face
2. Current use of investigational agents to prevent or treat COVID-19
3. Known liver disease (ALT/AST >3x ULN or diagnosis of cirrhosis)
4. Known renal disease (eGFR < 60 ml/min) or acute nephritis.
5. Uncontrolled hypertension (SBP>140 or DBP>90 while on medications)
6. Pregnant or breastfeeding women

Sub-study 1b mQFPD vs. placebo:

66 total patients (N=27 in each of two study arms: mQFPD and placebo plus an additional 20% per arm to guard against dropout) who have tested positive for COVID-19 and are mildly-to-moderately symptomatic will be included in the study.

#### **Inclusion Criteria**

1. Positive COVID-19 diagnosis within the prior 72 hours or within 9 days of symptom onset
2. Age 18 and older
3. Women of childbearing potential must have a negative urine or serum hCG. Women of childbearing potential must have a negative serum pregnancy test at screening and agree to use contraception throughout the study period.
4. Capable of documenting vitals, symptoms, and study product intake daily and communicating this information to the study team
5. Willing to minimize alcohol, cannabis and dairy products during the study period.

#### **Exclusion Criteria**

1. Any of the following symptoms which, according to the CDC, require hospitalization:
  - a. Trouble breathing
  - b. Persistent pain or pressure in the chest
  - c. New confusion or inability to arouse
  - d. Bluish lips or face
2. Current use of investigational agents to prevent or treat COVID-19
3. Prisoners
4. Known liver disease (ALT/AST >3x ULN or diagnosis of cirrhosis)
5. Known renal disease (eGFR < 60 ml/min) or acute nephritis.
6. Uncontrolled hypertension (SBP>140 or DBP>90 while on medications)
7. Pregnant or breastfeeding women
8. Allergy to tree nuts
9. Bleeding dyscrasia or on anticoagulation (aspirin and/or clopidogrel is allowed)
10. Use of Tolbutamide
11. Use of systemic corticosteroids (hydrocortisone, cortisone, prednisolone, betamethasone, methylprednisolone, prednisone, dexamethasone). Inhaled budesonide is to be allowed.
12. Use of digoxin
13. Use of Oxacillin
14. Use of Interferon

15. Use of Vincristine
16. Use of Cyclosporine
17. Use of Amiodarone
18. Patients with a past medical history of epilepsy
19. Use of monoamine oxidase inhibitors (MAOI)
20. Use of Methamphetamine within the prior 30 days
21. Use of Cocaine within the prior 30 days
22. Use of aminoglycosides, carbamazepine, flecainide, lithium, phenytoin, phenobarbital, rifampicin, theophylline and warfarin

Sub-study 1c Fo-Tv vs. placebo:

266 total patients who are receiving COVID-19 vaccination will be included in the study.

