- Group 1 – either Mycelium of *Fomitopsis officinalis* and *Trametes versicolor* (FoTv) for sub-studies 1a and 1c or modified Qing Fei Pai Du Tang (mQFPD) for sub-study 1b
- Group 2 - Inert placebo (encapsulated brown rice)

We anticipate screening approximately 90 or 75 potential candidates per sub-study in order to consent and enroll 66 or 48 participants to account for up to 20% drop-out rate.

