### **Sub-study 1c**

Once enrolled, all study participants will receive a package containing the following:

- Four day supply of study medication (capsules containing either FoTv or placebo)
- 
- Written instructions on proper usage of study medication
- Paper study daily diary, to include daily medication diary, symptom scores, and temperature/BP measurement data

During the trial period, participants will be verbally instructed on proper usage of study product and to assess their symptoms. Each participant will receive a paper copy and an emailed study daily diary to record symptoms and symptom scores, medication compliance, and any other medication use.

Participants will be asked to report to the study team any adverse events, either of the study medication or of the vaccination itself, including urgent care, emergency room, or hospitalization.

Subjects will be contacted by phone by the study team 2 weeks after vaccination # 1, 4 weeks after vaccination # 1, 2 weeks after vaccination # 2 (if applicable), 4 weeks after vaccination # 2 (if applicable), 6 months after baseline, and 12 months after baseline to report any symptoms.

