### **Control Product Dose and Route of Administration**

The placebo control has been developed by the mycelium supplier and contains freeze-dried cooked organic brown rice. It has been encapsulated to a cGMP standard. It has been packaged identically to the test products and appears identical to the verum product (FoTv or mQFPD) by an untrained study participant. Subjects will be instructed to take 8 capsules three times with the same dosing instructions as the study medication for each respective sub-study (1a, 1b, or 1c) as described above.

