#### **Inclusion Criteria**

1. Scheduled to receive COVID-19 vaccination
2. Age 18 and older

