#### **Exclusion Criteria**

1. Current use of investigational agents to prevent or treat COVID-19
2. Prisoners
3. Known liver disease
4. Known renal disease or acute nephritis.
5. Pregnant or breastfeeding women
6. Use of immunosuppressive medication

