#### Loss of confidentiality

### **15. RISK MANAGEMENT PROCEDURES AND ADEQUACY OF RESOURCES**

Subjects will be monitored throughout the study and their symptoms will be recorded and reviewed by the medical monitor on a daily basis during the active phase of treatment.

Safety of the study medication will also be assessed through laboratory data collection either at the end of the treatments (for non-hospitalized patients) or on hospital admission (utilizing labs on admission for hospitalized patients)

Study participants will be advised to report any skin eruptions to the study team and to stop medication immediately until they can be interviewed by our medical monitor who will make the assessment of allergy.

Respiratory allergies such as asthma exacerbations will be treated as COVID-19 exacerbations, where medication will be stopped and participants will be directed to immediate medical attention. An adverse event will be logged, and relation to the study medication will be determined per protocol.

In an event of participants requiring immediate medical attention, the study team will first refer the patient to contact their primary care physician if they are in close communication. If they are not, the study team will provide the participant with a short list of telephone numbers that patients can call to seek immediate medical attention. This will be specific to Southern California and will include 24-hour hotlines that are run by insurance companies, healthcare centers, and regional governments. If none are appropriate, they will be directed to dial 911.

All serious adverse events (SAEs) will, per UCSD IRB guidelines, be reported to the IRB and DSMB within 3 business days of learning of the event. The study biostatistician will send a tabulated symptom and adverse event report daily to all sites and to the study PI and weekly to the study DSMB and IRB.

Any adverse events, as well as any escalation of care, including urgent care, emergency room, or hospitalization, will be reported to the study team after appropriate medical care has been received, via a dedicated phone number or email address that is specific for urgent matters.

The UCSD site will implement a Data and Safety Monitoring Board (DSMB) to review data safety and monitoring as part of their responsibilities. The DSMB will include two senior researchers, and a consumer representative. They will have a conference call bi-weekly (or more frequently, if needed).

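### No eligibility list covers known allergy to the mushroom ingredients of FoTv or to the rice placebo, and allergy is not among the screening history items named

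*Combined protocol and SAP*

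**What the plan says.** Section 10 has a separate eligibility list for each sub-study. The 1b exclusions include, as item 8, "Allergy to tree nuts". The 1a exclusions have six items, none an allergy, and end with "Pregnant or breastfeeding women". The 1c exclusions also have six, none an allergy, and end with "Use of immunosuppressive medication". The 1c inclusion list has two entries, "Scheduled to receive COVID-19 vaccination" and a minimum age. The 1a and 1b inclusion lists do not mention allergy either.

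On the products, Section 9 defines the active group as "either Mycelium of *Fomitopsis officinalis* and *Trametes versicolor* (FoTv) for sub-studies 1a and 1c", with mQFPD in 1b. The placebo, common to all three sub-studies, "contains freeze-dried cooked organic brown rice". Active and placebo are both taken as 8 capsules three times a day, for 14 days in 1a and 1b and for 4 days in 1c.

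On screening, the targeted medical history (Section 9, Clinical Assessments, item 2) names bleeding, kidney and liver conditions, immune status, and pregnancy or breastfeeding. Allergy is not named.

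On reactions after dosing, Section 15 tells participants to report skin eruptions and "stop medication immediately until they can be interviewed by our medical monitor who will make the assessment of allergy". Respiratory allergies are handled as COVID-19 exacerbations: medication is stopped, the participant is sent for care, an adverse event is logged and its relation to study medication is determined.

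In 1c, dosing starts on the day of vaccination, and participants report adverse events "either of the study medication or of the vaccination itself".

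**The concern.** The plan anticipates allergic reactions to the capsules but provides for them only once they have happened. A volunteer who already knows of a mushroom or rice allergy could be identified with one question before randomisation. Nothing in the eligibility lists turns that person away, and nothing in the named history items prompts the question.

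Two things are at stake. The first is an avoidable risk to the participant, who takes the capsules without supervision. It carries some weight because the plan knows of no human clinical trial of Fo products (Section 7), finds no clinical safety data in the literature (Section 14, FoTv risk) and relies on this Phase 1 work to detect harm. The second applies to 1c. Capsules and vaccine begin on the same day and events from both are reported together, so a rash in one participant is hard to assign to either. Relation to study medication is recorded on the case report form and tabulated in the safety summary, so that assignment is reported data.

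**Working it through.** **1. Products set against exclusions.**

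| Sub-study | Active product | Placebo | Allergy exclusion |
|---|---|---|---|
| 1a | FoTv (mushroom mycelium) | Brown rice | None |
| 1b | mQFPD (21 herbs) | Brown rice | Tree nuts, both arms |
| 1c | FoTv (mushroom mycelium) | Brown rice | None |

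No row has a criterion for mushroom, rice or capsule ingredients. A volunteer with a known mushroom allergy who is otherwise suitable passes every item of the 1a and 1c lists.

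**2. Exposure.** Capsules per day: 8 × 3 = 24. Over the course: 24 × 14 = 336 in 1a and 1b, and 24 × 4 = 96 in 1c. The plan's rice figure (Section 14) reproduces: 24 × 0.5 g = 12 g a day, or 0.42 oz, which is just under half an ounce. Over 14 days that is 168 g, or 5.9 oz, against the 6 oz bowl it cites.

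**3. How many people.** The documents give no prevalence, so p, the share of volunteers with a relevant known allergy, is an assumption. Expected number = N × p. Chance of at least one = 1 − (1 − p)^N. N is 66 (1a) and 266 (1c), from Section 9.

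| Assumed p | 1a expected | 1a chance of ≥1 | 1c expected | 1c chance of ≥1 |
|---|---|---|---|---|
| 0.1% | 0.07 | 6.4% | 0.27 | 23.4% |
| 0.5% | 0.33 | 28.2% | 1.33 | 73.6% |
| 1% | 0.66 | 48.5% | 2.66 | 93.1% |
| 2% | 1.32 | 73.6% | 5.32 | 99.5% |

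Allocation is 1:1, so about half of those sensitised to only one product would receive it: 0.03 to 0.66 people in 1a and 0.13 to 2.66 in 1c. The halving assumes that the allergen is in one arm's capsules only.

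**4. Weight of one event.** 1/33 = 3.0% of a 1a arm; 1/133 = 0.75% of a 1c arm.

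**5. Effect on the 1c comparison.** Participants are randomised with equal probability, blinded, and vaccinated in both arms. Vaccine reactions are therefore expected equally in both arms, and a between-arm difference reflects the capsules. What remains uncertain is the cause of a single participant's event. No sample size, power or alpha figure depends on this point.

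**The case against.** The strongest reply is that allergy is already handled. Section 15 has stop-and-assess rules. The case report form records relation to study medication. Section 14 reports very low consumer adverse event rates for the mushrooms and no known risk from this amount of rice. The history item is introduced as a non-exhaustive list, so allergies may be asked about in practice. People who know of a mushroom allergy are also unlikely to join a trial with mushrooms in its working title after a consent discussion.

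Much of this stands, and it limits the size of the point. It does not close the gap. The Section 15 rules begin after a reaction, general tolerability says little about people with a known allergy, and self-selection is not a criterion. The Section 15 respiratory rule is also worded for people with COVID-19, so its application to 1c vaccinees is unstated.

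A reader might infer several stronger things that the documents do not support:

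- **That the vaccine confounds the 1c comparison.** It does not, for the reason in step 5 of the working. An excess of product reactions in the FoTv arm is what a safety comparison should show.
- **That 1a merges allergy with worsening disease.** Section 15 also requires an adverse event record and a relatedness decision, so the rule governs immediate action and not classification.
- **That the lists contradict one another.** Section 9 ties the extra 1b exclusions to its herbal components, and Section 14 refers to a herb-by-herb safety appendix not seen here. Tree nuts may be specific to that formula, so their absence from 1a and 1c is no error. The exclusion also covers the 1b placebo arm.
- **That a few severe reactions would dominate the safety reading.** Nothing in the documents indicates their frequency or severity.

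**Conclusion.** The gap is real but small. On the text, known allergy to an ingredient of the active product or placebo is neither an exclusion nor a named screening question in any sub-study; the sole exception in kind is tree nuts in 1b. The consequences are an avoidable risk to a few participants and, in 1c, weaker attribution of individual events. Under an assumed prevalence of 0.1% to 2%, about 0.3 to 5 people in 1c and 0.1 to 1.3 in 1a would be affected, roughly half of them allocated to the product concerned. These counts illustrate scale and are not estimates from the documents. Randomised comparisons, sample size, power and alpha are unaffected. Severity is minor to moderate: the case for acting is that the risk is preventable at almost no cost, not that the trial's conclusions are threatened.

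**What to change.** Reconcile the three eligibility lists in Section 10 with the products described in Section 9 and with the allergy rules in Section 15. Known allergy to an ingredient of the active product or placebo should be asked about in the screening history and treated as an eligibility criterion in each sub-study. The sponsor's clinicians should set the wording and decide which ingredients it covers. For 1c, also state how relatedness to capsule or vaccine is judged for an individual event, and how the Section 15 respiratory rule applies to participants who do not have COVID-19.

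The cost is about one eligibility line per sub-study, one screening question and the loss of a few volunteers. No analysis or sample size changes.
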